### 3.2 Design and Procedure

This is a phase 2 study that will accrue patients with WHO grade IV recurrent malignant glioma (glioblastoma or gliosarcoma) in two cohorts to assess the efficacy of Sym004. Cohort 1 will include patients who are non-bevacizumab failures; whereas, Cohort 2 will include patients who have progressed after prior treatment with bevacizumab (bevacizumab-failure). Both cohorts will accrue simultaneously, with 36 subjects in Cohort 1 and 25 subjects in Cohort 2 (see Section 13.8 for justification of sample size). All patients will be treated with Sym004, a recombinant antibody mixture that specifically binds to EGFR. For that reason, only patients whose tumor is determined to be EGFR-amplified (i.e. greater than 15% of cells exhibiting > 5 copies of EGFR loci) will be accrued on this study.

Prior to Amendment 31, approximately 25 subjects received Sym004 at 18 mg/kg intravenously every two weeks. After the approval of Amendment 31, subjects who enroll on study will receive Sym004 at 24 mg/kg intravenously every 2 weeks. A total of 65 additional subjects (36 in Cohort 1 and 29 in Cohort 2) will be treated at the 24 mg/kg dose level. In addition, subjects who enrolled at the 18 mg/kg dose and who tolerated this dose of Sym004 well (i.e. no skin toxicities  $\geq$  grade 3) will have the option to increase their dose to 24 mg/kg upon approval of Amendment 31. A treatment cycle will be 4 weeks. The patients will have repeat MRIs of the brain every 8 weeks.

The accrual of the first 3-6 patients at the 24 mg/kg dose level, regardless of cohort assignment, will be at a controlled rate for initial safety monitoring. Details concerning this initial accrual at the 24 mg/kg dose level can be found in Section 13.7.4.

For an exploratory objective, we will determine EGFRvIII status at baseline for all patients using archival tumor tissue. If a subject has more than one source of archival or frozen tissue, each source may be requested to determine if EGFRvIII expression has changed over time.

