## 7 INVESTIGATIONAL PLAN

### 7.1 Study Design

This is a phase 2 study that will accrue patients with WHO grade IV recurrent malignant glioma (glioblastoma or gliosarcoma) in two cohorts to assess the efficacy of Sym004. Cohort 1 will include patients who are non-bevacizumab failures; whereas, Cohort 2 will include patients who have progressed after prior treatment with bevacizumab (bevacizumab-failure). Both cohorts will accrue simultaneously, with a goal of 36 subjects in Cohort 1 and 25 subjects in Cohort 2 (see Section 13.8 for justification of sample size). All patients will be treated with Sym004, a recombinant antibody mixture that specifically binds to EGFR. For that reason, only patients whose tumor is determined to be EGFR-amplified will be accrued on this study.

Prior to Amendment 31, approximately 25 subjects received Sym004 at 18 mg/kg intravenously every 2 weeks. After the approval of Amendment 31, subjects who enroll on study will receive 24 mg/kg intravenously every 2 weeks. A maximum of 65 additional subjects (36 in Cohort 1 and 29 in Cohort 2) will be treated at the 24 mg/kg dose level. In addition, subjects who enrolled at the 18 mg/kg dose and who tolerated this dose of Sym004 well (i.e. no skin toxicities  $\geq$  grade 3) will have the option to increase their dose to 24 mg/kg upon approval of Amendment 31. A treatment cycle will be 4 weeks. The patients will have repeat MRIs of the brain every 8 weeks. Subjects with CR, PR, or stable disease may continue on study as long there is no evidence of disease progression or toxicities as described in Section 10.8.1.

The accrual of the first 3-6 patients at the 24 mg/kg dose level, regardless of cohort assignment, will be at a controlled rate for initial safety monitoring. Details concerning this initial accrual at the 24 mg/kg dose level can be found in Section 13.7.4.

For an exploratory objective, we will determine EGFRvIII status at baseline for all patients using archival tumor tissue. If a subject has more than one source of archival or frozen tissue, each source may be requested to determine if EGFRvIII expression has changed over time.

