#### 13.4.2 Statistical Hypothesis, Model, and Method of Analysis

Based upon the Kaplan-Meier estimator, the proportion of patients who are alive and progression-free 6 months after initiation of Sym004 treatment will be estimated. Details about the hypothesis test that will be conducted is provided in Section 13.8.

The primary analyses will focus on the dose group to which the patient was originally assigned. No more than 2 of the patients treated initially at the 18 mg/kg dose will have their dose escalated to 24 mg/kg. Efficacy analyses will be generated with and without these patients to assess the impact of these patients with dose escalation on inferences.

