### 13.5.1 Key Secondary Objective: Safety

Within each cohort and dose level, the proportion of patients who experience grade 3, 4, or 5 adverse events that are possibly, probably, and definitely related to protocol treatment will be estimated.

In addition, for each type of toxicity, the maximum grade experienced by each patient will be summarized with frequency distributions. Two adverse experience tabulations will be generated, one that includes all toxicities regardless of attribution, and one that includes only toxicities that are possible, probably, and definitely related to Sym004 treatment.

Patients who have their dose escalated from 18 mg/kg to 24 mg/kg will be included in toxicity summaries for 18 mg/kg and 24 mg/kg. The toxicity experienced prior to dose escalation will be summarized with the other patients treated at the 18 mg/kg dose level; whereas, the toxicity experienced after dose escalation will be included in the summary of adverse events associated with 24 mg/kg.

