### 13.7.2 Interim Efficacy Analysis for 24 mg/kg Sym004

With Amendment 31, the design of the study will be modified. Within each cohort, a two-stage study design is used to assess outcome. The statistical properties of this design are provided in section 13.8.2. However, the stopping rules for each cohort are summarized below. After stage 1 enrollment is completed, accrual will be temporarily suspended while data from the first stage matures unless at that point 1 or more patients have survived 6-months progression-free.

Patients who have their dose escalated from 18 mg/kg to 24 mg/kg will not be considered in these interim efficacy analyses for 24 mg/kg Sym004.

Monitoring Rules		
	Cohort 1	Cohort 2
Statistical Hypothesis	PFS6 $\leq$ 20% vs PFS6 $\geq$ 40%	PFS6 $\leq$ 3% vs PFS6 $\geq$ 20%
Stage 1	Accrue 19 patients	Accrue 12 patients
Criteria for Accrual to Stage 2	>3 patients who live 6+ months progression-free	>0 patients who live 6+ months progression-free
Stage 2	Accrue 17 more patients	Accrue 17 more patients

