### 13.7.4 Initial Toxicity Monitoring among Patients Treated with 24 mg/kg Sym004

Given limited experience with 24 mg/kg Sym004, the first 3-6 patients will be slowly accrued and carefully monitored for unacceptable toxicity (see Section 7.1.2).

The first patient, regardless of cohort, will be treated and observed for 1 cycle before the accrual of a second patient. During this period of observation, the patient will receive at minimum 2 full doses of Sym004 and be followed until the end of Cycle 1. If the patient experiences an unacceptable adverse event (refer to Section 7.1.2), the study will be suspended and the patient's experience will be discussed with Symphogen to determine whether patient accrual should continue. Otherwise, 2 additional patients will be treated.

The second and third patient can be accrued at the same time. However, further accrual after the 3rd patient is suspended until completion of 1 cycle of therapy. After the first 3 patients have been observed, the number of patients with unacceptable toxicity will be determined.

- If none of the first 3 patients has an unacceptable toxic event, accrual will continue without further slowed accrual.
- If 2 of the first 3 patients has an unacceptable toxicity, the study will remain suspended. Results will be discussed with Symphogen with the expectation that accrual will be terminated.
- If 1 of the first 3 patients has an unacceptable toxicity, an additional 3 patients can be accrued after which accrual will be suspended until all patients have been observed for at least 1 cycle. If none of the additional 3 patients experiences an unacceptable toxicity, then accrual will resume without the requirement of staggered entry. If 1 of these 3 patients experiences an unacceptable toxicity, the study will remain suspended while a discussion occurs with Symphogen to determine if accrual is terminated.

For initial monitoring of the 24 mg/kg dose of Sym004, an unacceptable adverse event is defined as any grade 3, 4, or 5 adverse event that is definitely, possibly, or potentially related to Sym004 treatment.

Patients who have their dose escalated from 18 mg/kg to 24 mg/kg will be considered as part of this interim analyses of toxicity at the 24 mg/kg if they are among the first 3 (or 6) patients who receive Sym004 at the 24 mg/kg dose level.

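### Up to 2 of the first 3 patients in the 24 mg/kg safety check may have been escalated after tolerating 18 mg/kg, which can tilt the check toward ending staggered entry

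*Combined protocol and SAP*

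**What the plan says.** Because experience with 24 mg/kg is limited, 13.7.4 provides that "the first 3-6 patients will be slowly accrued and carefully monitored for unacceptable toxicity". One patient is observed for a cycle, then two more. With no unacceptable event in the first 3, staggered entry ends. With one, 3 more patients are treated, and staggered entry ends if none of those has an event. The last definition given in 13.7.4 counts any grade 3-5 event considered related to Sym004.

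Patients escalated from 18 mg/kg "will be considered as part of this interim analyses of toxicity at the 24 mg/kg if they are among the first 3 (or 6") treated at 24 mg/kg. Section 3.2 limits escalation to patients "who tolerated this dose of Sym004 well (i.e. no skin toxicities" of grade 3 or worse). Section 7.1 says that they "will have the option to increase their dose to 24 mg/kg upon approval of Amendment 31", which is also when new enrolment at 24 mg/kg opens. Section 13.4.2 sets the ceiling: "No more than 2 of the patients treated initially at the 18 mg/kg dose will have their dose escalated to 24 mg/kg".

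Elsewhere these patients are handled differently. For efficacy, 13.7.2 states: "Patients who have their dose escalated from 18 mg/kg to 24 mg/kg will not be considered in these interim efficacy analyses", and 13.8.2 does the same for the final 24 mg/kg assessment. For safety, 13.5.1 says that "the toxicity experienced after dose escalation will be included in the summary of adverse events associated with 24 mg/kg". Sections 13.4.2 and 13.5.2 ask for efficacy results with and without escalated patients; 13.5.1 asks for no such comparison for toxicity.

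**The concern.** The check is meant to protect up to 65 patients who start at 24 mg/kg with no lead-in at 18 mg/kg. An escalated patient differs from them in three ways: no severe skin reaction at the lower dose, when skin reactions are the drug's most frequent adverse event (7.1.3); still on treatment; and already past the first exposure. No section sets a minimum number of new starters in the check or plans a look at it without escalated patients.

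If escalated patients carry a lower risk of a related grade 3-5 event, a decision resting on 3 patients, two of them pre-selected, will end staggered entry more often than the same rule applied to new starters. The same patients would pull the 24 mg/kg toxicity proportion in 13.5.1 slightly downward.

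**Working it through.** The plan gives no operating characteristics for the 13.7.4 rule, so there is no figure of its own to reproduce.

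**Inputs from the documents**
- Rule (13.7.4): pass on 0 of 3, or on 1 of 3 followed by 0 of 3.
- At most 2 escalated patients (13.4.2).
- Up to 65 new patients at 24 mg/kg: 36 in Cohort 1 and 29 in Cohort 2. Stage 1 of Cohort 2 has 12 (13.7.2, 13.8.2).
- At 18 mg/kg, 2 of the first 19 patients had grade 3 skin toxicity (7.2).

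**Inputs assumed**
- p is the risk of a counted event in a new starter, and q the risk in an escalated patient. The documents give neither.
- Accrual continues after discussion if the first patient has an event.

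**Step 1: composition.** New starters number at least 3 − 2 = 1 of the first 3, and at least 6 − 2 = 4 of the first 6. Escalated patients are at most 2/3 = 67% at the first decision and 2/6 = 33% after expansion.

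**Step 2: chance of passing.** With two escalated patients in the first 3 and new starters after that:
- P0 = (1−q)²(1−p)
- P1 = 2q(1−q)(1−p) + (1−q)²p
- Pass = P0 + P1 × (1−p)³

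At p = 0.40, (1−p)³ = 0.216:

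| q | P0 | P1 | Pass |
|---|---|---|---|
| 0.40 (equal risk) | 0.216 | 0.432 | 0.309 |
| 0.30 | 0.294 | 0.448 | 0.391 |
| 0.20 | 0.384 | 0.448 | 0.481 |
| 0.10 | 0.486 | 0.432 | 0.579 |

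With new starters only, the result is the first row, 0.309.

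**Step 3: other values of p, with q = p/2.** New starters only against two escalated patients: 0.709 against 0.805 at p = 0.2; 0.494 against 0.641 at p = 0.3; 0.172 against 0.340 at p = 0.5.

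**Step 4: sensitivity to the continuation assumption.** Suppose instead that an event in the first patient ends the check. At p = 0.4, new starters only give 0.216 + 0.6 × (2 × 0.4 × 0.6) × 0.216 = 0.278. With two escalated patients at q = 0.2, one of them first, the result is 0.384 + 0.8 × (0.2 × 0.6 + 0.8 × 0.4) × 0.216 = 0.460. The levels fall, but the gap (18 points) is close to that in Step 2 (17 points).

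**Step 5: the 13.5.1 proportion.** Take a wide contrast, 50% in new starters and 10% in two escalated patients:
- All 65: (65 × 0.5 + 2 × 0.1)/67 = 32.7/67 = 48.8%.
- Both in Cohort 1: (36 × 0.5 + 0.2)/38 = 47.9%.
- Both in Cohort 2: (29 × 0.5 + 0.2)/31 = 47.4%.
- Both in Cohort 2 stopped at stage 1: (12 × 0.5 + 0.2)/14 = 44.3%.

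**The case against.** A reader might infer that the check can be filled entirely with escalated patients and so never test the target population. The documents do not support that: the ceiling in 13.4.2 leaves at least one new starter in the first 3 and four in the first 6. Two is also a maximum. Escalation is optional, and 16 of the first 19 patients at 18 mg/kg had already come off study for progression (7.2).

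A reader might also infer that the bias is established and large. It is not. Selection is on skin toxicity alone, whereas the check counts any related grade 3-5 event, including hypomagnesemia and infusion reactions. In this trial's own data the skin criterion would have removed about 2 of 19 patients. Earlier exposure could even raise the risk of cumulative toxicity, which would reverse the direction. The effect therefore starts at zero and cannot be sized from the documents.

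Two further readings go too far. Passing does not declare 24 mg/kg safe; it ends staggered entry, and individual dose modification, re-treatment criteria and continuing toxicity assessment still apply. Nor does excluding these patients from efficacy while including them in safety contradict itself. PFS6 runs from the first Sym004 dose, so their exposure is mixed for that endpoint, whereas toxicity after escalation does occur at 24 mg/kg.

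Whether an escalated patient could be the very first patient observed is unclear. Section 13.7.4 does not rule it out, but its wording about Cycle 1 and accrual fits a new enrollee better.

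These points limit the size of the concern. They leave standing that two of the three patients behind the first decision may be tolerance-selected.

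**Conclusion.** The concern holds as a weakness of design whose size the documents leave open. Under 13.7.4 with 13.4.2, up to 2 of the first 3, or 2 of the first 6, may be escalated patients. If their risk of a related grade 3-5 event is below that of new starters, the check is biased toward ending staggered entry. At an assumed 40% new-starter risk, with both escalated patients in the first 3 and accrual continuing after any first-patient event, the excess chance of passing runs from zero at equal risk to 27 percentage points (58% against 31%) at a 10% risk in escalated patients.

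One part needs no assumption about risk: as few as one of the first 3 would come from the population that the check protects. The effect on the 13.5.1 summary is minor, about 1 percentage point over 65 patients even at 50% against 10%. It is 2 to 3 points if both fall in one fully accrued cohort, and about 6 points if both fall in Cohort 2 and it stops at stage 1.

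**What to change.** - **Section 13.7.4:** count only patients whose first Sym004 dose is 24 mg/kg toward the first 3 (or 6). Review related grade 3-5 events in escalated patients alongside, in the same discussion with Symphogen, but do not let an event-free course in an escalated patient fill a place. No safety signal is lost.
- **Section 13.5.1:** report the 24 mg/kg toxicity proportion with and without escalated patients, matching what 13.4.2 and 13.5.2 already require for efficacy.

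The change is about a sentence in each section. The cost is up to 2 more staggered new entries before accrual opens fully. Those patients count toward the planned 65, so the total sample size does not change.

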## 13.8 Sample Size Calculation

### 13.8.1 Sample Size Requirements for 18 mg/kg Sym004

The sample size requirements within each cohort of patients will be considered separately.

*Non-Bevacizumab Failures (Cohort 1):* In a recent phase 3 study among patients with recurrent glioblastoma, a PFS6 rate of 19% (approximate 95% confidence interval: 12% - 30%) was observed for patients treated with lomustine. If the true PFS6 associated with SYM004 is comparable to that seen with lomustine or approximately 20%, there is limited interest in further investigation of SYM004 in this patient population. However, if the true PFS6 is 40% or greater, there is interest in further investigation of the experimental treatment within this patient population. With 36 patients, there is 90% power to differentiate between a PFS6 rate of 20% and 40% assuming a test conducted at the 0.1 level of significance (1-tailed). If 11 or more patients of the 36 patients live more than 6 months without disease progression, the treatment will be considered worthy of further investigation in this patient population.

*Bevacizumab Failure (Cohort 2):* A recent publication from the Preston Robert Tisch Brain Tumor Center reported a PFS6 rate of 2.3% (95% CI: 0.2, 10.4) among patients who received non-bevacizumab treatment after progression on bevacizumab treatment administered in the recurrent setting. If the true PFS6 associated with SYM004 within this patient population is comparable to that observed in this publication or about 3%, there is limited interest in further investigation of the agent in this setting. However, if the true PFS6 rate is 20% or greater, there is interest in further clinical investigation. With 25 patients, there is 90% power to differentiate between a PFS6 rate of 3% and 20% assuming a test conducted at the 0.1 level of significance. If 3 or more patients of the 25 live more than 6 months without disease progression, the treatment is worthy of further investigation.

### 13.8.2 Sample Size Requirements for 24 mg/kg Sym004

Prior to Amendment 31, the original goal was to accrue 61 subjects to receive 18 mg/kg Sym004, with 36 patients in Cohort 1 and 25 in Cohort 2. After the approval of Amendment 31, no additional subjects will be enrolled at 18 mg/kg.

After Amendment 31, the effect of 24 mg/kg Sym004 treatment on PFS6 will be assessed in two cohorts with a maximum of 36 patients in Cohort 1 and 29 in Cohort 2. With Amendment 31, the design of the study will be modified. Within each cohort, either a two-stage minimax or two-stage optimal design will be used to assess PFS6. The same benchmarks that were used with 18 mg/kg Sym004 are used here with the same targeted type I and II error rates (i.e.  $\alpha = \beta = 0.1$ ).

Patients originally treated at the 18 mg/kg dose level who have their dose escalated to 24 mg/kg will not be considered in these analyses.

**Non-Bevacizumab Failures (Cohort 1):** A minimax two-stage design will test the hypothesis that the true PFS is 20% or less versus the alternative that the true PFS is 40% or greater. After testing the treatment on 19 patients in the first stage, the trial will be terminated if 3 or fewer patients live 6 months or more progression-free. Otherwise, additional patients will be accrued so a total of 36 patients will be treated. If the total number of patients living 6 months or more progression-free is less than or equal to 10, then the treatment is rejected as not worthy of further investigation in this patient population. The expected sample size of 28.26 and the probability of early termination is 0.455. The type I and II error rates are 0.086 and 0.098, respectively.

**Bevacizumab Failure (Cohort 2):** An optimal two-stage design will be used to test the hypothesis that the true PFS is 3% or less versus the alternative that the true PFS is 20% or greater. After testing the treatment on 12 patients in the first stage, the trial will be terminated if 0 patients live 6 months or more progression-free. Otherwise, the trial will continue and a total of 29 patients will be studied. If 2 or more patients live 6 months or more progression-free the treatment will be considered worthy of further investigation. The expected sample size of 21.64 and the probability of early termination is 0.561. The type I error rate is 0.038 and the type II error rate is 0.10.

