#### 13.4.3 Handling of missing values, censoring, and discontinuations

The sample size justification provided in Section 13.8 assumes that all patients will be followed for their clinical status for at least 6 months or until death. Historical data within the Preston Robert Tisch Brain Tumor Center suggests that such an assumption is fully achievable. If patients are lost to follow-up prior to their 6-month outcome, estimates of PFS6 will be appropriately adjusted for such censoring in the estimation of the outcome from the Kaplan-Meier estimator.

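### Cohort 2 at 24 mg/kg: declaring success at 2 or more of 29 has a type I error of 0.153 against a 0.10 target, and the quoted type I error, early-termination probability and expected sample size belong to a different design

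*Combined protocol and SAP*

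**What the plan says.** Section 13.8.2 (Combined protocol and SAP) calls the Cohort 2 design at 24 mg/kg an optimal two-stage design. The hypothesis is that "the true PFS is 3% or less versus the alternative that the true PFS is 20% or greater". On error rates it says: "The same benchmarks that were used with 18 mg/kg Sym004 are used here with the same targeted type I and II error rates", which it gives as 0.1 for each.

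Stage 1 has 12 patients and the cohort stops if none is progression-free at 6 months; otherwise 29 are studied. The monitoring table in Section 13.7.2 agrees: 12 patients, then 17 more if there are ">0 patients who live 6+ months progression-free". That table has no final cutoff. The only one for this cohort and dose is in Section 13.8.2: "If 2 or more patients live 6 months or more progression-free the treatment will be considered worthy of further investigation".

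The paragraph then gives the operating characteristics: "The expected sample size of 21.64 and the probability of early termination is 0.561", and "The type I error rate is 0.038 and the type II error rate is 0.10".

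For comparison, the 18 mg/kg single-stage design in Section 13.8.1 used the same benchmarks for this cohort and required 3 or more successes in 25.

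**The concern.** Two things look wrong. First, the 24 mg/kg rule asks for fewer successes (2) from more patients (29) than the 18 mg/kg rule (3 of 25), with the same null, alternative and targets. The two-stage design's early stop for futility lowers the false-positive rate, but perhaps not by enough to allow that.

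Second, with 12 patients and a stop at zero, the early-termination probability depends only on 12 and the null rate. The printed 0.561 does not fit a null of 3%.

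At stake is the only final decision rule for the primary endpoint in bevacizumab failures at 24 mg/kg. If the cutoff is too lenient, an inactive drug passes more often than the plan allows, while the report carries a false-positive rate that the rule does not have. Low counts are a realistic prospect: Section 7.2 reports that, of the first 19 patients at 18 mg/kg across both cohorts, only one completed six months of therapy before progression.

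**Working it through.** **Inputs.** From Section 13.8.2: null p0 = 0.03, alternative p1 = 0.20, target type I and type II errors 0.10 each, n1 = 12, stop at 0, total n = 29 (so n2 = 17), success at k = 2 or more. Section 13.4.3 allows PFS6 to be treated as a fully observed yes/no outcome, since the sample size "assumes that all patients will be followed for their clinical status for at least 6 months or until death".

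**Formulas.** X1 and X2 are the successes in stages 1 and 2.

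- Early termination: PET = P(X1 ≤ r1), where r1 is the stage 1 stopping bound; with r1 = 0 this is (1 − p0)^n1
- Expected sample size: EN = n1 + n2 × (1 − PET)
- P(success) = sum over x1 > r1 of P(X1 = x1) × P(X2 ≥ k − x1)

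**Check of the method on Cohort 1.** With 19 patients, stop at 3 or fewer, then 36 and success at 11 or more, 20% against 40%: PET 0.4551, EN 28.26, type I 0.0861, type II 0.0976. The plan states 0.455, 28.26, 0.086 and 0.098, so all four reproduce.

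**Cohort 2, PET and EN.** PET = 0.97^12 = 0.694. EN = 12 + 17 × (1 − 0.6938) = 17.20. The plan states 0.561 and 21.64. The two printed figures also disagree with each other for 12/29: a PET of 0.561 would give EN = 12 + 17 × 0.439 = 19.46.

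**Cohort 2, type I error at p = 0.03.** Stage 1: P(X1 = 1) = 0.2575, P(X1 = 2) = 0.0438, P(X1 ≥ 2) = 0.0486, P(X1 ≥ 3) = 0.0048. Stage 2: P(X2 ≥ 1) = 0.4042, P(X2 ≥ 2) = 0.0909.

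- Success at 2 or more: 0.2575 × 0.4042 + 0.0486 = 0.1527
- Success at 3 or more: 0.2575 × 0.0909 + 0.0438 × 0.4042 + 0.0048 = 0.0460 (from unrounded terms)

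The same sums at p = 0.20 give power, and cutoff 4 is added for comparison:

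| Final rule, 12 then 29 | Type I | Power | Type II |
|---|---|---|---|
| 2 or more (as written) | 0.1527 | 0.9266 | 0.0734 |
| 3 or more | 0.0460 | 0.9005 | 0.0995 |
| 4 or more | 0.0096 | 0.8286 | 0.1714 |

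Only 3 or more meets both targets.

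**Where the printed figures come from.** An exhaustive search of two-stage designs (total below 45) for 3% against 20% with both errors at most 0.10 gives:

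| Design | Stage 1 | Total | Success at | PET | EN | Type I | Type II |
|---|---|---|---|---|---|---|---|
| Optimal | 0 of 12 stops | 29 | 3 or more | 0.6938 | 17.20 | 0.0460 | 0.0995 |
| Minimax | 0 of 19 stops | 25 | 3 or more | 0.5606 | 21.64 | 0.0377 | 0.0997 |
| Printed in 13.8.2 | 0 of 12 stops | 29 | 2 or more | 0.561 | 21.64 | 0.038 | 0.10 |

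The printed stage sizes are those of the optimal design, and the printed PET, EN and type I error are those of the minimax design. The printed type II error of 0.10 fits either design at 3 or more, but not the written rule. Under 19/25, success at 2 or more would also miss the target, with type I error 0.1650.

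**The result that changes class.** The probability of passing stage 1 and finishing with exactly 2 successes is 0.1527 − 0.0460 = 0.107 at 3%, and 0.9266 − 0.9005 = 0.026 at 20%.

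**The case against.** The strongest point is that the excess depends on the null rate. Section 13.8.1 cites a historical PFS6 of 2.3%, and at 2.3% the written rule has a type I error of 0.0998, just inside 0.10. That is correct, but the plan rounds the benchmark to 3% and makes 3% or less the null, so the error has to be judged at 3%.

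Second, the plan never states 3 or more of 29, so the intended cutoff is inferred. The likeliest explanation is that the optimal design's rejection bound (2 or fewer is not worthy) was written down as the success cutoff; the Cohort 1 paragraph uses the rejection form. The documents do not prove this, and confirmation is needed. But both designs that could have been meant require 3 or more.

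Third, Section 13.4.2 estimates PFS6 by Kaplan-Meier, whereas this calculation uses counts. The decision rule is itself a count, and Section 13.4.3 assumes complete 6-month follow-up, so counts are the right basis.

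Fourth, the consequence is bounded. This is an uncontrolled phase 2 screen, the stage 1 rule and the sample size are unaffected, and only a result of exactly 2 successes changes class. This stands as a limit on the effect; it does not make the rule meet its target.

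**Conclusion.** The point holds on both counts.

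As written, the Cohort 2 rule at 24 mg/kg has a type I error of 0.153. A drug with a true PFS6 of 3% would be called worthy of further investigation about once in 6.5 trials (1/0.1527), against a limit of once in 10. That is 3.3 times the error of the same design with a cutoff of 3 (0.1527/0.0460).

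The printed type I error, early-termination probability and expected sample size do not describe a 12/29 design at this cutoff or at 3 or more. Early termination at the null is understated (0.561 against 0.694) and expected sample size overstated (21.64 against 17.20).

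This rests on a null of 3%, a one-sided test and known 6-month status for every patient. The problem is confined to Cohort 2. Because it affects a primary-endpoint decision threshold, it must be corrected.

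**What to change.** First, the sponsor's statistician should confirm from the sample-size software output which design was intended. The repeated 12, 17 and 29, and the word optimal, favour 12/29.

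**If 12/29 is confirmed,** replace the last three sentences of the Cohort 2 paragraph in Section 13.8.2 with text such as:

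> Sym004 will be judged worthy of further study in this cohort if at least 3 of the 29 patients are alive and progression-free at 6 months, and not worthy if 2 or fewer are. With a true PFS6 of 3%, the probability of early termination is 0.694 and the expected sample size is 17.20. The type I error is 0.046 and the type II error is 0.0995.

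Optionally, add a final-rule row to the Section 13.7.2 table: Cohort 1, 11 or more of 36; Cohort 2, 3 or more of 29. The cost is three sentences and, if wanted, one table row. Power goes from 92.7% to 90.05%, which still meets the 90% target, and no patients are added.

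**If 19/25 was intended,** the cutoff is still 3 or more and the printed operating characteristics stand. The edit is then wider: the design becomes minimax, the stage sizes change in Sections 13.7.2 and 13.8.2, and the totals of 29 and 65 change wherever they appear (Sections 3.2, 7.1, the opening of 13, and 13.8.2), with 65 becoming 36 + 25 = 61.

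In either case, make the correction before Cohort 2 outcomes at 24 mg/kg are known, so that the cutoff cannot appear to have been chosen from the data.
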